9.1.2 Hypotheses

The primary study hypothesis was that implementation of a bundled DSI targeting the respiratory culturing pathway would not associate with significant increases in adverse safety outcomes.

The secondary study hypotheses were that implementation of a bundled DSI targeting the respiratory culturing pathway would associate with reductions in rates of respiratory culture positivity (RCP) and ICU-antimicrobial utilization rates (ICU-AURs).

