4 OBJECTIVES AND ENDPOINTS

OBJECTIVES	ENDPOINTS	JUSTIFICATION FOR ENDPOINTS
Primary		
To determine the safety of a multi-faceted ventilator-associated pneumonia diagnostic stewardship bundle.	
Mortality per 1000 mechanically-ventilated patient days
 
Ventilator-associated events (using Centers for Disease Control/National Healthcare Safety Network definitions) per 1000 patient days
 
Median duration of mechanical ventilation per patient.
	The goal of this study is to demonstrate preliminary safety of a diagnostic stewardship bundle for ventilator-associated pneumonia.
Secondary		
To determine the association between a multi-faceted ventilator-associated pneumonia diagnostic stewardship bundle and ICU antibiotic utilization rates.	
Total ICU antibiotic utilization rates (total antibiotic days of therapy per 1000 mechanically-ventilated patient days).
 
Broad-spectrum ICU antibiotic utilization rates (broad-spectrum antibiotic days of therapy per 1000
	Our preliminary data suggests that a bundled diagnostic stewardship intervention can successfully reduce antibiotic use in mechanically-ventilated patients.

OBJECTIVES	ENDPOINTS	JUSTIFICATION FOR ENDPOINTS
	mechanically-ventilated patient days).	
To determine the association between a multi-faceted ventilator-associated pneumonia diagnostic stewardship bundle and rates of positive respiratory cultures.	Positive respiratory cultures per 1000 mechanically-ventilated patient days.	
To assess study feasibility and adherence to protocolized intervention.	Respiratory cultures ordered per 1000 mechanically-ventilated patient days Percentage of respiratory cultures obtained by BAL Percentage of respiratory cultures from BAL samples with alveolar neutrophils <50%	Adherence to study intervention is crucial to evaluating study efficacy and potentially recalibrating approach to intervention prior to multi-center implementation.

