8 END-OF-INTERVENTION/END-OF-STUDY

8.1 DISCONTINUATION OF INTERVENTION

The full diagnostic stewardship intervention will be discontinued at the primary study completion date (February 2023). The study interventions will also be halted for prespecified increases in adverse safety outcomes (noted previously).

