9 STATISTICAL CONSIDERATIONS

9.1 GENERAL STATISTICAL APPROACH

9.1.1 Descriptives

We will compare categorical variables by reporting frequencies and percentages and assess statistical significance using a chi-square test. Subject-level continuous variables will be compared using Kruskal-Wallis tests. Rate variables (e.g., deaths per 1,000 MVPDs) will be compared using a z-score test.

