9.2 ANALYSIS OF THE PRIMARY AND SECONDARY ENDPOINT(S)

Primary and secondary study outcomes will be compared between patient cohorts before and after DSI implementation. All primary/secondary study outcomes will compare patients admitted to study ICUs over the course of the year-long study intervention (Feb 2022-23) versus those admitted in the pre-intervention historical control period (Feb 2017-22). As above, rate variables will be compared using a z-score test. A p-value of 0.05 will be utilized for statistical significance.

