9.3 EXPLORATORY ANALYSES

In addition to unadjusted pre- vs post- outcome comparisons, we will utilize additional analytic approaches to explore exposure-outcome relationships between the study DSI and ICU antimicrobial use. These will include: 1) interrupted time series analyses of rates at the calendar month level to account for changes in temporal trends antecedent to the time of the intervention, 2) individual subject-level negative binomial analyses with a covariate for admitted pre vs. post intervention date.

For the interrupted time series analysis, will treat each calendar month (beginning as the unit of analysis. Each month will have an average antibiotic DOT per mechanically-ventilated patient per day. Linear regression will be used to model change over time, as well as an interaction for the change over time before and after the start of the trial intervention date.

Subject-level analyses will also be performed to account for confounding clinical variables impacting ICU antimicrobial use. We will utilize patient-level data from pre-intervention historical control data to construct a multivariate model predictive of ICU-AURs. For these analyses, all study subjects will have a calculated rate of ICU-AURs (e.g., total antibiotic DOTs on mechanical ventilation divided by total number of person days on mechanical ventilation). Multiple imputation using fully conditional specification will be performed to create 25 imputation data sets to account for missing data, and negative binomial regression models were constructed for each data set using backwards selection. Covariates will be retained in a final multivariate master model if they are retained in 100% of negative

binomial regression models, after evaluation for multicollinearity. Admission before or after the study intervention will then be to the final model as a covariate to determine the independent effect of the study intervention on antibiotic use.

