9.4 OTHER ANALYSES

9.4.1 Safety Analyses

This study will utilize a Data and Safety Monitoring Board (DSMB) comprised of study personnel (the study PI, biostatistician, and ICU medical directors, [name]), as well as an independent medical monitor ([name], Chief of Division of Allergy, Immunology and Infectious Diseases at Robert Wood Johnson University Hospital). [name] has served on data safety and monitoring committees for multiple federally- and industry-funded clinical trials, many of which have involved the study of ventilator-associated pneumonia.

The DSMB will meet every two months to review the following safety metrics: 1) Mortality per 1000 mechanically-ventilated patient days per ICU, Ventilator- associated events (using Centers for Disease Control/National Healthcare Safety Network definitions) per 1000 mechanically-ventilated patient days per ICU, Median duration of mechanical ventilation per patient per ICU. All safety outcomes will be compared to preintervention ICU data collected over the last 5 years to ensure that postintervention values fall within 2 standard deviations of preintervention controls. The study will be halted if any safety outcome is increased by more than 2 standard deviations relative preintervention control data. If safety outcomes are decreased by more than 2 standard deviations relative to preintervention control data (i.e. in a favorable direction following the intervention), the study intervention will be continued as this is a single-arm study trial design.

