9.4.2 Sub-Group Analyses

We will also perform a series of prespecified confirmatory subgroup analyses for all study outcomes, stratified by individual study ICU and DSI implementation phase (for the latter, in order to account for seasonality, outcomes in the post-intervention cohort were compared to historical control patients admitted to study ICUs during analogous months in the pre-intervention control period).

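### The primary safety conclusion rests on finding no significant increase, and the plan asks for no interval showing how large an increase the data leave open

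*Combined protocol and SAP*

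**What the plan says.** Section 4 names safety as the primary objective, with three endpoints: mortality rate, ventilator-associated event rate and median duration of ventilation. Its justification reads: "The goal of this study is to demonstrate preliminary safety of a diagnostic stewardship bundle for ventilator-associated pneumonia". Section 9.1.2 then words the primary hypothesis as the bundle one that "would not associate with significant increases in adverse safety outcomes".

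Section 9.2 compares the one-year intervention cohort (February 2022 to 2023) with the five-year historical cohort (February 2017 to 2022). Rates are compared by a z-score test. For measures such as ventilation duration, section 9.1.1 says: "Subject-level continuous variables will be compared using Kruskal-Wallis tests". The decision level is: "A p-value of 0.05 will be utilized for statistical significance". Whether that level is one- or two-sided is not stated.

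Three other sections bear on the point:

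- Section 9.3 adds an interrupted time series and covariate-adjusted models, but limits their purpose: "we will utilize additional analytic approaches to explore exposure-outcome relationships between the study DSI and ICU antimicrobial use".
- Section 9.4.2 says: "We will also perform a series of prespecified confirmatory subgroup analyses for all study outcomes, stratified by individual study ICU and DSI implementation phase". In the phase analyses it matches calendar months to deal with seasonality.
- Section 9.4.1 has the monitoring board meet every two months under this rule: "The study will be halted if any safety outcome is increased by more than 2 standard deviations relative preintervention control data". Section 8.1 refers back to it.

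**The concern.** A hypothesis that no significant increase will be seen is supported by failing to reject. The fewer the events, the easier that is. A difference test at 0.05 limits false alarms; it does not limit the size of an increase that goes unnoticed. A confidence interval does, and the plan does not ask for one.

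This is the primary objective, and section 3.1.1 itself names underdiagnosis as a potential risk of the intervention (section 3.1.3 calls it theoretical). A report that gives only non-significant p-values for the three endpoints would not tell readers whether a small or a large increase remains compatible with the data. The same tests are carried into the ICU and phase subgroups, where counts are smaller and the analyses are labelled confirmatory.

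**Working it through.** **Reading the sections together.** Section 4 gives the goal (show preliminary safety), 9.1.2 the hypothesis (no significant increase), and 9.1.1 and 9.2 the tools (z-score test, Kruskal-Wallis, 0.05). I looked elsewhere for something that bounds the final effect:

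- Section 9.3 covers antimicrobial use only.
- Section 9.4.2 applies to all outcomes and handles seasonality in the phase comparisons, but adds no interval and does not address secular trend or case mix.
- Section 9.4.1 compares observed values with a 2-SD limit during conduct. It does not say what the SD is taken over (months, two-month blocks, years or patients), and nothing makes it the test for the final conclusion.

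**Size, as an illustration.** The plan has no sample size, event count or baseline rate, so there is no figure of its own to reproduce.

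Inputs from section 9.2: one year against five years, and a level of 0.05.

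Assumptions: equal ventilator days each year, so E expected events in the intervention year if nothing changes and 5E historical events; Poisson counts; two-sided test.

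*Chance that a true 20% increase is non-significant.* SE(log ratio) = √(1/(1.2E) + 1/(5E)), and the chance is Φ(1.96 − ln 1.2/SE), with ln 1.2 = 0.1823.

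- E = 30: SE = √(1/36 + 1/150) = 0.186; Φ(1.96 − 0.98) = 0.84
- E = 100: SE = √(1/120 + 1/500) = 0.102; Φ(1.96 − 1.79) = 0.57
- E = 300: SE = √(1/360 + 1/1500) = 0.059; Φ(1.96 − 3.11) = 0.13

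A simulated pooled z-test on Poisson counts gives 0.82, 0.57 and 0.14. If 0.05 were one-sided, replacing 1.96 by 1.645 gives 0.75, 0.44 and 0.07.

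*What a non-significant result can leave open.* Upper 95% limit = ratio × exp(1.96 × √(1/post + 1/pre)).

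| E | Largest non-significant post count (pre count) | Observed ratio | Upper 95% limit | Upper limit if observed ratio is 1.00 |
|---|---|---|---|---|
| 30 | 42 (150) | 1.40 | 1.97 | 1.48 |
| 100 | 121 (500) | 1.21 | 1.48 | 1.24 |
| 300 | 337 (1500) | 1.12 | 1.26 | 1.13 |

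The last column is exp(1.96 × √(1.2/E)).

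*Subgroups.* If one ICU or one phase holds half the events (E = 15, 50, 150), the first formula gives 0.90, 0.76 and 0.41.

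I give no figure for ventilation duration, because the documents give nothing about its distribution.

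**The case against.** The best defence is that this is a pilot. Section 2.2 describes the aim as collecting preliminary data, section 4 speaks of preliminary safety, and 9.1.2 is a hypothesis rather than a decision rule. Intervals can be calculated from the same data at any time, and a separate safety rule runs throughout the trial. Much of this stands. It removes any need for formal power or a margin, and it makes this a matter of analysis and reporting rather than of design. It does not supply the missing estimate, because the plan neither asks for intervals nor rests the conclusion on them.

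A reader might infer more than the documents support:

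- *That the plan declares p > 0.05 to mean safe.* No section says so. The point is that the hypothesis and tests, followed as written, lead there.
- *That safety has no quantified limit at all.* Section 9.4.1 has one for conduct. Because its SD is undefined, its protection cannot be worked out from the documents, but that is no ground for treating it as worthless.
- *That this safety result decides whether a multi-center trial goes ahead.* The remark on multi-center implementation in section 4 justifies the adherence objective, not the safety one.
- *That a large harm is likely to be missed.* All event counts above are assumed, and the highest percentages come from the smallest counts.

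**Conclusion.** The point holds as a gap in how the primary safety conclusion is to be reached. The final comparison can return support for preliminary safety without saying what increase it has failed to exclude, and no other section repairs this. That reading rests on the text and does not depend on any assumed number.

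Its practical size does depend on counts the documents do not give. Under the stated assumptions it is substantial at about 100 or fewer expected events in the intervention year and modest at about 300 or more. Sampling error is also not the whole uncertainty: for the safety endpoints, secular trend and case mix between 2017-22 and 2022-23 remain unaddressed, and an interval will not correct for them. The change should be made before the safety results are interpreted.

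**What to change.** In sections 9.1.2 and 9.2, base the primary safety conclusion on estimates and keep the planned tests beside them:

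1. For mortality and ventilator-associated events, report the post/pre rate ratio with its 95% confidence interval, and the event counts behind it.
2. For ventilation duration, report the difference in medians with a bootstrap 95% interval, resampling patients. Note that this interval will be coarse if duration is recorded in whole days.
3. For each endpoint, state the largest increase not excluded, and state that p > 0.05 does not establish safety.
4. Say beside the intervals that they reflect sampling error only, because the comparison with 2017-22 is unadjusted.
5. Apply the same reporting to the safety subgroups in section 9.4.2.

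No non-inferiority margin is needed for the pilot. The cost is some rewording and one bootstrap, with no new data. The downside is that some endpoints will have to be reported as inconclusive rather than safe.

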9.2 ANALYSIS OF THE PRIMARY AND SECONDARY ENDPOINT(S)

Primary and secondary study outcomes will be compared between patient cohorts before and after DSI implementation. All primary/secondary study outcomes will compare patients admitted to study ICUs over the course of the year-long study intervention (Feb 2022-23) versus those admitted in the pre-intervention historical control period (Feb 2017-22). As above, rate variables will be compared using a z-score test. A p-value of 0.05 will be utilized for statistical significance.

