1 PROTOCOL SUMMARY

1.1 SYNOPSIS

[figure not shown]
Title:	Implementation of a Diagnostic Stewardship Bundle for Ventilator-associated Pneumonia among Mechanically-ventilated patients: a pilot/feasibility trial.
Grant Number:	Not applicable
Study Description:	A pilot/feasibility trial to evaluate the safety and efficacy of a multi-faceted ventilator-associated pneumonia diagnostic stewardship bundle. Trial ICUs will sequentially implement interventions targeting the respiratory culture diagnostic testing pathway to minimize diagnostic error and overtreatment of ventilator-associated pneumonia.
Objectives:	
Primary Objective: To determine the safety of a multi-faceted ventilator-associated pneumonia diagnostic stewardship bundle.
 
Secondary Objectives:
 
- To determine the association between a multi-faceted ventilator-associated pneumonia diagnostic stewardship bundle and ICU antibiotic utilization rates.- To determine the association between a multi-faceted ventilator-associated pneumonia diagnostic stewardship bundle and rates of positive respiratory cultures.
Endpoints:	To assess study feasibility and adherence to protocolized intervention.
	
Primary Endpoints:
 
- Mortality per 1000 mechanically-ventilated patient days- Ventilator-associated events (using Centers for Disease Control/National Healthcare Safety Network definitions) per 1000 patient days- Median duration of mechanical ventilation per patient.
	
Secondary Endpoints:
 
- Positive respiratory cultures per 1000 mechanically-ventilated patient days.- Total ICU antibiotic utilization rates (total antibiotic days of therapy per 1000 mechanically-ventilated patient days).- Broad-spectrum ICU antibiotic utilization rates (broad-spectrum antibiotic days of therapy per 1000 mechanically-ventilated patient days).- Respiratory cultures ordered per 1000 patient days.- Percentage of respiratory cultures obtained by BAL.- Percentage of respiratory cultures from BAL samples with alveolar neutrophils <50% (for Phase 2 only)
Study Population:	All mechanically-ventilated patients hospitalized within Michigan Medicine Cardiac Care Unit (CCU) and Critical Care Medicine Unit (CCMU).

Phase or Stage:	Pilot/feasibility trial of a population-based intervention.
Description of Sites/Facilities Enrolling Participants:	2 Michigan Medicine Intensive Care units.

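### The headline before/after tests pool the two ICUs with no ICU term, so a change in the ICU mix could shift any outcome on which the units differ

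*Combined protocol and SAP*

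**What the plan says.** The trial runs in "2 Michigan Medicine Intensive Care units", the CCU and the CCMU. Section 9.2 gives the headline analysis: "Primary and secondary study outcomes will be compared between patient cohorts before and after DSI implementation". The cohorts are all ventilated patients in the study ICUs in Feb 2022-23 and in Feb 2017-22. For rates, "As above, rate variables will be compared using a z-score test". Section 9.1.1 adds chi-square and Kruskal-Wallis tests. None of these is given an ICU stratum, and section 9.3 itself describes the pre/post comparisons as unadjusted.

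Section 9.3 adds two exploratory analyses, both of antibiotic use only. In the interrupted time series, "Each month will have an average antibiotic DOT per mechanically-ventilated patient per day"; the regression terms are time and a change in slope at the intervention. The subject-level negative binomial model lists no candidate covariates and keeps those that survive backward selection in every imputed data set.

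ICU does appear elsewhere. The DSMB metrics in section 9.4.1 include "Mortality per 1000 mechanically-ventilated patient days per ICU", with ventilator-associated events and ventilation duration also reviewed by unit. Section 9.4.2 prespecifies analyses of all outcomes "stratified by individual study ICU and DSI implementation phase" and calls them confirmatory.

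**The concern.** A pooled rate is a weighted average of the two unit rates, with each unit's share of the denominator as its weight. A cardiac unit and a medical critical care unit may well differ in antibiotic use, mortality or ventilation time, and nothing in a single-arm, five-years-against-one comparison holds the shares fixed. If the shares move, the pooled result moves too, and the change would be credited to the bundle. A shift towards the lower-use unit would look like an antibiotic reduction; a shift the other way would mask one. This is separate from calendar trend and from case mix within a unit.

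The plan already plans to report by ICU, yet the tests that bear on the hypotheses in section 9.1.2 are the crude pooled ones. The three primary safety outcomes have no adjusted analysis at all, because section 9.3 covers antimicrobial use only.

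**Working it through.** **Inputs.** From the documents: two ICUs; five control years against one intervention year; significance level 0.05. There is no figure to reproduce, because the documents give no unit rates, unit shares, ventilated days or event counts. Everything else below is assumed.

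**Mechanism.** Let units A and B have fixed rates rA and rB, and let s be B's share of the denominator. The pooled rate is (1 − s)·rA + s·rB. With no change inside either unit, the pooled change is (s_post − s_pre)·(rB − rA). It is zero if rA = rB or if s does not change.

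**Size of the shift.** Set rA = 1, rB = RR and s_pre = 0.30. The relative change is Δs·(RR − 1) / (0.70 + 0.30·RR).

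| RR | Δs = 5 points | Δs = 10 points | Δs = 15 points |
|---|---|---|---|
| 1.3 | 0.015/1.09 = 1.4% | 0.030/1.09 = 2.8% | 0.045/1.09 = 4.1% |
| 1.5 | 0.025/1.15 = 2.2% | 0.050/1.15 = 4.3% | 0.075/1.15 = 6.5% |
| 2.0 | 0.050/1.30 = 3.8% | 0.100/1.30 = 7.7% | 0.150/1.30 = 11.5% |

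The sign reverses if the shift is towards the lower-rate unit.

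**Antibiotic days of therapy (DOT).** Assume 900 and 600 DOT per 1000 ventilated days, with the lower-use unit going from 30% to 40% of days, and 20,000 days before and 4,000 after.
- Before: 0.7 × 900 + 0.3 × 600 = 810. After: 0.6 × 900 + 0.4 × 600 = 780. Change −3.7%.
- Poisson z, unpooled variance: −0.030 / √(0.810/20,000 + 0.780/4,000) = −1.95. With pooled variance it is −1.93. Both have two-sided p just above 0.05.
- An expected z of that size still means rejection in about half of repetitions (49% to 50%), with no change in either unit. DOT cluster within patients, so this figure reflects Poisson variance only; the −3.7% does not depend on that.
- The Mantel-Haenszel rate ratio by ICU is 1.00. If DOT rose 2% in both units, the pooled rate would still fall, to 780 × 1.02 = 796 against 810, while the Mantel-Haenszel ratio would be 1.02.

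**Mortality.** Assume 25 deaths per 1000 ventilated days pooled before, the same day counts, and a 10-point shift from 30% towards the higher-rate unit. The post rate is 25 × 1.0275 = 25.7, 25 × 1.0435 = 26.1 or 25 × 1.0769 = 26.9 for RR 1.3, 1.5 or 2.0. The expected z is 0.25, 0.39 or 0.68 (unpooled variance), and two-sided rejection is 5.7%, 6.8% or 10.5%.

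**Median ventilation duration.** Here the weights are patients, not days. Assume log-normal durations with medians of 3 and 5 days and log-SD 1. A 30% share of days for the longer-stay unit is (0.3/5) / (0.3/5 + 0.7/3) = 20% of patients; a 40% share is (0.4/5) / (0.4/5 + 0.6/3) = 29%. The pooled median goes from 3.32 to 3.46 days, a shift of 0.14 days.

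**The case against.** The strongest reply is that ICU results are already promised. Section 9.4.2 reports every outcome by unit and calls these analyses confirmatory, and with only two units those results would show directly whether either had changed. On safety, the DSMB looks at each ICU every two months against its own history, with a halting rule, so detection of harm does not rest on the pooled test alone. This stands, and it narrows the point. It does not remove it: two separate results are not a combined adjusted estimate, and nothing says which result prevails if the pooled and per-ICU answers differ.

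A reader might infer that any shift in ventilated days moves every pooled outcome. The documents do not support that. An outcome moves only if the units differ on it and its own denominator mix changes, and neither is shown. Nor are ventilated days always the weight: the median is weighted by patients and the BAL percentages by cultures.

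The reading of section 9.3 is also partly inference. That the monthly series is a single pooled one is the natural reading, but the sentence defining the unit of analysis is incomplete. With no candidate covariates listed, ICU might be offered and kept, and backward selection would tend to keep it if it strongly predicts antibiotic use. It is simply not guaranteed.

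**Conclusion.** The point holds in conditional form. The headline section 9.2 contrasts have no ICU adjustment, and they are open to a composition effect if the units differ on an outcome and their shares change. Under the assumptions shown, a 10-point shift moves pooled rates by about 3% to 8%. That matters mainm for antibiotic use, where counts are large and a spurious change of this size sits at the edge of significance. For mortality the inflation is modest, about 6% to 10% against 5%. If the mix is stable, the bias is zero and the stratified and crude results will nearly agree.

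It would be tempting to conclude that the plan will produce a false antibiotic reduction or hide harm. The documents do not support either: they contain no unit rates or shares, and both the per-ICU analyses and the per-ICU safety review would help expose such an effect. What is missing is an ICU-adjusted headline estimate and a rule for disagreement.

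**What to change.** - **Section 9.2.** Make the headline estimates ICU-stratified and state that they are the ones used for the section 9.1.2 hypotheses. For rates, use a Mantel-Haenszel rate ratio, or a rate model with an ICU term and a log-denominator offset. For percentages, use Mantel-Haenszel. For ventilation duration, use a van Elteren test, with medians shown by unit.
- **Section 9.3.** Force ICU into the subject-level model. Build the monthly series from ICU-months with at least an ICU intercept.
- **Section 9.4.2.** Keep the per-ICU results as the display of the strata, and say how a disagreement with the crude pooled result will be read.

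The cost is SAP wording and slightly more analysis work; the plan already calls for results by ICU, so no new data are needed. Fitting a separate trend for each ICU would lose some precision with only 12 post-intervention months, so ICU-specific trends can be optional.

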5 STUDY DESIGN

5.1 OVERALL DESIGN

We plan to conduct a quasi-experimental, single-arm pilot/feasibility trial of a VAP diagnostic stewardship bundle in the MM Critical Care Medicine Unit (CCMU) and Cardiac Care Unit (CCU). This is a population-based rather than individual intervention. Both the CCMU and CCU will designate team leaders (one faculty member, fellow, and unit nurse), who will be instructed on study design and rationale, to disseminate study information and education in concert with study PI to colleagues through use of infographics and powerpoint-based sessions.

The study intervention will consist of interventions at all 3 phases of the diagnostic testing pathway (see Section 7 for full details). The bundle's first two interventions (ordering & collection phase interventions) will be implemented at the onset of the study period. The final bundled intervention (reporting phase) will be implemented 6 months after study onset (see Study Timeline (section 1.2)).

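### The primary safety comparison is unadjusted against controls centred three years earlier, and the trend and case-mix analyses in 9.3 are planned for antibiotic use only

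*Combined protocol and SAP*

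**What the plan says.** The primary objective is safety (section 4), and the primary hypothesis in 9.1.2 is that the bundle "would not associate with significant increases in adverse safety outcomes".

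- **Primary comparison (9.2).** All primary and secondary outcomes are compared between the intervention year and controls: "versus those admitted in the pre-intervention historical control period (Feb 2017-22). As above, rate variables will be compared using a z-score test". The z-score test covers mortality and ventilator-associated events. Ventilation duration falls under 9.1.1: "Subject-level continuous variables will be compared using Kruskal-Wallis tests". No covariate or time term is named, and 9.3 itself calls these comparisons unadjusted.
- **Further models (9.3).** Two are planned, to "explore exposure-outcome relationships between the study DSI and ICU antimicrobial use". The first is an interrupted time series by calendar month, with antibiotic days of therapy as its outcome. The second is a negative binomial model for antimicrobial utilization: "Subject-level analyses will also be performed to account for confounding clinical variables impacting ICU antimicrobial use".
- **Safety monitoring (9.4.1).** "All safety outcomes will be compared to preintervention ICU data collected over the last 5 years". This is done per ICU, again without adjustment.
- **Subgroups (9.4.2).** All study outcomes, safety included, are stratified by ICU and by implementation phase. For the phases, "outcomes in the post-intervention cohort were compared to historical control patients admitted to study ICUs during analogous months in the pre-intervention control period", in order to allow for seasonality.

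**The concern.** A before/after comparison attributes to the intervention anything else that changed between the two periods. Section 9.3 recognises the two main threats, prior trend and clinical confounding, and plans for both. It does so for a secondary outcome and not for the primary one.

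The direction of the hypothesis makes this matter. Success is the absence of a significant increase in harm. If a safety rate was already falling, or patients were becoming less sick, a real increase could be offset and the bundle read as safe. If the rate was rising, a harmless bundle could look unsafe. The planned safety comparisons cannot tell these cases apart.

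**Working it through.** **1. Gap between periods (from the documents' dates).** Feb 2017 to Feb 2022 is centred on Aug 2019, and Feb 2022 to Feb 2023 on Aug 2022. The gap is 36 months. Matching calendar months over all five control years leaves it unchanged: the same months of 2017 to 2021 average to 2019, against 2022. Section 9.4.2 does not say whether all five years are used; pooling them is the natural reading.

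**2. What a trend alone does.** The plan gives no rate, trend, event count or power figure, so there is nothing to reproduce and every input from here on is assumed. With yearly change g, constant denominators and no bundle effect, the raw rate ratio is (1+g)^5 divided by the mean of (1+g)^k for k = 0 to 4.

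| g per year | Calculation | Raw ratio |
|---|---|---|
| -2% | 0.9039 / 0.9608 | 0.94 |
| -5% | 0.7738 / 0.9049 | 0.86 |
| -10% | 0.5905 / 0.8190 | 0.72 |
| +5% | 1.2763 / 1.1051 | 1.15 |

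If the month-matched phases used only the last control year, ±5% would give 0.95 and 1.05.

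**3. False signal of harm.** The SE of the log ratio is sqrt(1/E1 + 1/E0), with E1 the intervention-year events and E0 the five-year control events (Poisson, two-sided 5%). Take +5% a year, no effect and a control average of 200 events a year. Then E0 = 1000, E1 = 231 and SE = 0.0730. The log ratio of 0.144 gives z = 1.97, so a significant increase is found about 50% of the time. Depending on which year the count refers to, the range is 45-55%. For 100 events a year it is 25-31%, and for 400 it is 74-84%.

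**4. Masked harm.** Take a true 20% increase, -5% a year and 200 events a year. The expected raw ratio is 1.2 × 0.855 = 1.03, and it is significant about 5% of the time. A Poisson segmented model (trend, level and slope change, effect at the midpoint of the post-period) detects the increase 39-49% of the time, provided the baseline is log-linear.

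**5. Ventilation duration.** Simulation used a rank test, lognormal durations, 300-600 patients a year, log-SD 0.8-1.2 and 1,500 trials per cell. A +5% yearly drift with no effect was significant in 48-97% of runs. A true 20% lengthening with a -5% drift was significant in only 5-13%.

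**6. Case mix within an ICU.** If a group with twice the death rate goes from 40% to 30% of ventilated days, the raw ratio is 1.3/1.4 = 0.93 with no effect; the reverse shift gives 1.4/1.3 = 1.08. If the two groups were simply the two ICUs, the stratification in 9.4.2 would remove this.

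**7. What adjustment costs.** With no trend and no effect, the segmented model's SE is 1.31 times the raw one (0.1016 against 0.0775 at 200 events a year). Power for a true 20% increase falls from 72% to 46.5%. The model also depends on the shape of the baseline. If control months 37-60 run 15% high, the control mean is (36 + 24 × 1.15)/60 = 1.06. With no effect the raw ratio is 1/1.06 = 0.94, but the model gives 0.84. With a true 20% increase the raw ratio is 1.13 (41% detection) and the model gives 1.00 (3%).

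**The case against.** The strongest reply has three parts.

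*The safety outcomes are not compared only with one pooled block.* This is right. A reader of 9.2 alone might infer that nothing else is planned for them, but 9.4.2 stratifies every outcome by ICU and by phase with month-matched controls, and 9.4.1 reviews safety per ICU. What stands is narrower: none of these addresses secular trend or patient mix within an ICU.

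*The size is hypothetical, and this is a pilot.* Only the 36-month gap comes from the documents. A reader might infer from the illustrations that the planned result will be biased, or biased towards safety. The documents do not support that, because they do not report which way any safety rate was moving. Section 4 aims at preliminary safety, and 9.3 labels even the antibiotic models exploratory. This argues for a supporting analysis, not for a new primary one. There is no contradiction in the plan to correct.

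*Adjustment can mislead.* It can, as step 7 shows. A reader might want the adjusted estimate to replace the raw comparison, or to block a safety conclusion once it passes a cut-off. Neither is justified. The documents give no basis for a cut-off. With an illustrative 1.10 at 200 events a year, such a rule would lower correct findings of no increase from 98% to 83% per outcome when there is neither effect nor trend. Under the non-linear baseline it would barely change the false ones (58% to 57%).

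**Conclusion.** The concern holds in this form: the primary comparison of all three safety outcomes is unadjusted against controls centred three years earlier. Apart from the ICU and month-matched phase subgroups, no analysis addresses trend or patient case mix for them. This follows from the text with high confidence.

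Its practical effect is unknown. A background change of 5% a year, if present, would move a raw rate ratio by about 15% in either direction. That assumes a steady log-linear trend and constant denominators; the detection figures also assume Poisson counts at the stated volumes. It is worth fixing because it bears on the trial's primary question and the remedy is cheap.

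**What to change.** In 9.3, add the primary safety outcomes as prespecified supporting (sensitivity) analyses:

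1. **Mortality and ventilator-associated events:** a monthly segmented count model with an offset for the endpoint's own denominator and autocorrelation-robust standard errors. For ventilator-associated events, first settle that denominator: section 4 uses patient days and 9.4.1 uses ventilated patient days.
2. **Mortality (keeping the ventilated-day denominator) and ventilation duration:** patient-level models with calendar time, a pre/post term and prespecified case-mix covariates available at or before the start of ventilation.
3. **Baseline shape:** one check for non-linearity, such as a spline or a shorter control window.

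Keep the raw 9.2 comparison and the 9.4.2 subgroups, report the adjusted estimates with confidence intervals beside them, and interpret the safety result in light of both. State which control years the month-matching in 9.4.2 covers. The phase results stay useful because, by 5.1, "The final bundled intervention (reporting phase) will be implemented 6 months after study onset": a 20% increase confined to months 7-12 averages to about 10% over the year.

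The cost is SAP wording, a covariate list and modest analysis on data arranged by month and by patient, as 9.3 already plans for antibiotic use. Section 9.3 names no covariates, so the availability of suitable ones for mortality and duration has to be confirmed. Adjusted intervals will be wider (SE about 1.3 times the raw one, more with overdispersion). Because the segmented model is sensitive to a non-linear baseline, it must not replace the raw comparison.
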